#### ***6.3.1.1 Timing and volume of data collection for excluded subjects.***

If the subject is excluded from the study at his/her request, the investigator should try to find out the reason for the termination of the study. If the study is terminated due to the occurrence of AE/SAE, monitoring of the subject continues until AE/SAE resolution. In case of premature termination of the patient's participation in the study, the patient is invited to the study site to carry out the procedures of premature study termination visit (carried out within the frameworks of unscheduled visit); if the patient refuses to visit the study site, the premature study termination visit is carried out by phone, while as much as possible the available information is recorded.

#### **6.3.2 Terms and conditions of stopping/termination by the subject of treatment with the medicinal product under study**

Patients stop taking the study medicinal products upon completion of their participation in the study in accordance with the protocol or upon their exclusion from the study.

#### **6.3.3 Replacing the discontinued patients**

Replacement of the patients who discontinued their study participation is not provided.

## **7. Information about the medicinal products used in the clinical study**

### **7.1 Investigational medicinal product and reference product**

**Investigational medicinal product:** LRG-002

**Manufacturer:** Lek d.d., [name].

**Dosage form, dosage:** capsules

**Description:** Each capsule contains live lyophilized probiotic bacteria of Lactobacillus genus.

**Composition per 1 capsule:** each capsule contains at least  $1 \times 10^{10}$  CFU of Lactobacillus rhamnosus GG as a lyophilizate.

Excipients: sucrose, maltodextrin, silicon dioxide, magnesium stearate, sodium ascorbate

Capsule shell: hydroxypropyl methylcellulose, titanium dioxide (E171), gellan gum, water.

**Reference product:** Placebo

#### **Duration of treatment**

Patients will take the investigational medicinal products in all groups daily for 14 days.

### **7.2 Compliance control**

Compliance will be controlled by review of patient's diary and counting the amount of the medicinal product remaining.

### **7.3 Allowed concomitant treatments**

Oral beta-lactam antibiotic (eg, amoxicillin, amoxicillin + clavulanic acid, cefixime, etc.) (See Background antibacterial therapy) according to inclusion criterion 3, at the same dosage as at the study initiation.

Continuation of the drug administration, started prior to the inclusion into the study for treatment of concomitant diseases and not covered by any exclusion criterion. Female participants taking oral contraceptives may continue to take them during the study.

Standard symptomatic treatment agents used to treat acute respiratory infections (in case of medical need), including anilides, triazole derivatives, with the exception of drugs that can induce a laxative effect (for example, throat lozenges with sugar substitutes).

Agents for relieving symptoms of acute diarrhea (in case of medical need), including electrolyte solutions, with the exception of sorbents.

Prescribing therapy for acute diarrhea and symptomatic therapy for ARDs is possible only by the decision of the Investigator.

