### **6.3 Exclusion Criteria**

#### **6.3.1 Timing and terms of subject exclusion from the study**

Subjects can be excluded from the study of their own free will at any time without explanation, as well as by decision of the physician investigator or Sponsor, in cases where continued participation in the study poses a threat to the health and/or life of the patient. In addition, the patient will not be able to continue participating in the study for the following reasons:

Subject participation will be stopped in case any of the following reasons occur:

1. Disease progression (including pyrexia above 38°C for 3 days or longer);
2. Positive results of culture or PCR for the dysentery group, typhoid fever group, pathogenic E. coli and other pathogenic groups (incl. Cl. difficile), the treatment of which requires the prescription of additional antibiotic therapy;
3. Need to change tactics of antibacterial therapy (extension course of antibacterial therapy or change of antibiotic group);

4. The Ethics Committee, regulatory authorities, or Sponsor can terminate the clinical study or participation of the specific trial site in the study for any reason;
5. The investigator decided that the patient must be withdrawn from the study for the own interests of the patient;
6. Informed consent withdrawal (patient reluctance to continue to participate in the study);
7. Individual intolerability of Investigational medicinal products according to Investigator's judgment;
8. Occurrence of clinically significant adverse event or serious adverse event in the patient;
9. Patient's non-compliance;
10. Error enrollment (e.g., the patient was included with violation of the inclusion/non-inclusion criteria);
11. The patient complies with the non-inclusion criteria during the study;
12. The patient receives/requires an additional treatment which might influence the study results or patient's safety (see "Prohibited concomitant therapy" section);
13. Other conditions or events which, in the Investigator's judgement, require the patient's exclusion from the study.

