#### **7.4 Prohibited concomitant therapy**

1. Systemic glucocorticosteroids within last 8 weeks prior to and during the study;
2. Any antibacterial agents in the last 3 months prior to the study and during the study, excluding the antibacterials according to inclusion criterion 3 during the study;
3. Use of any proton pump inhibitor within 3 months prior to the study;
4. Use of other probiotics (bacteria or yeast, medications, food supplements, fermented products) and the product Broncho-munal® within 2 weeks prior to and during the study;
5. Any therapy (including medications, medical devices and food supplements) that can influence the stool consistency must not be used, according to the Investigator's opinion, within 14 days prior to Visit 1 (excluding the drugs specified in items 3 and 4 of the “Allowed Concomitant Treatments”).

The list of prohibited medicinal products is presented in Appendix 1

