## 17. Appendices

### 17.1 Appendix 1. Prohibited Therapy List

| Pharmaceutical groups              | Active substance   |
|---|---|
| Systemic glucocorticosteroids             | hydrocortisone, cortisone, prednisone, methylprednisone, prednisone, triamcynolone, dexamethasone, betamethasone and their analogues and/or combinations and derivatives thereof  |
| Antibacterial agents                      | aminoglycosides, amphenycols, ansamicines, glycopeptides, carbapenemes, lincosamides, macrolides and azalides, penicillins, tetracyclines, cephalosporins - in monotherapy and/or combinations  |
| Probiotics, including dietary supplements | acidophilic lactobacteria, kefir fungi, bifidobacteria bifidum, Escherichia coli, lactobacteria, lysozyme, enterococcus fecium, longum bifidobacteria, animalis bifidobacteria, lactulose, plantharum lactobacteria, product Broncho-munal ® - as monotherapy and as part of the drug / dietary supplement in any combination                                      |
| Adsorbents                                | activated carbon, aluminium oxide, attapulgate, colloidal silicon dioxide, lactulose, lignin hydrolysed, povidone, polymethylsiloxane polyhydrate, dioctahedral smectite - as monotherapy and as a part of the drug / dietary supplements in any combination  |
| Calcium preparations                      | calcium glubionate, calcium lactobionate, calcium carbonate, calcium lactogluconate - as monotherapy and as part of the drug / dietary supplement in any combination  |
| Anti-diarrheal medications                | attapulgate, bergenia rhizome, bacillus subtilis, bifidobacteria bifidum, snakeweed rhizome, burnet rhizome with roots, loperamide+symeticone, loperamide, oval plantain seed coating, racecadotryl, dioctahedral smectite, hackberry fruit, blueberry fruit - as monotherapy and as part of the drug / dietary supplements in any combination                                |
| Myotropic spasmolytics                    | bendazole, metamizole, papaverine, drotaverine, theobromine, bencyclane, darifenacin, dicycloverine, codeine, camylophin, mecloxamine, propyphenazole, ergotamine, mebeverine, oxybutynin, otilonium bromide, platyphylline, pynaverium bromide, trimebutine, as well as plant spasmolytics - as monotherapy and as part of the drug / dietary supplements in any combination |

|  |   |
|--|---|

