Antidiarrheal medicinal products	Attapulгите, Bergenia rhizoma, Bacillus subtilis, Bifidobacterium bifidum, Snakeweed rhizoma, burnet rhizomes with roots, loperamide + simethicone, loperamide, plantain oval seed coat, Racecadotril, Dioctahedral smectite, fruits of bird cherry, fruits of common blueberries – as monotherapy and as part of a medicinal product/ dietary supplement in any combination

Myotropic antispasmodics	Bendazole, metamizole, papaverine, drotaverine, theobromine, bencyclan, darifenacin, dicycloverine, codeine, camilofin, mecloxamine, propyphenazone, ergotamine, mebeverine, oxybutynin, otilonium bromide, platyphylline, pinaverium bromide, trimebutine as well as herbal antispasmodics – as monotherapy and as part of a medicinal product/ dietary supplement in any combination
Antiemetics and medicinal products affecting gastrointestinal motility	Pyridostigmine, neostigmine, itopride, cisapride, aprepitant, bromopride, granisetron, dimenhydrinate, domperidone, levomenthol solution in menthyl isovalerate, meclozine, moxastine, ondansetron, palonosetron, perphenazine, thiethylperazine, trifluoperazine, tropisetron, fosaprepitant as well as herbal medicinal products – as monotherapy and as part of a medicinal product/ dietary supplement in any combination

7. Efficacy analysis

Analysis of efficacy endpoints will be carried out in accordance with Section V of the Recommendations of the Board of the Eurasian Economic Commission *On Guidelines on the Principles of Applying Biostatistics in Clinical Trials of Medicines* No. 19 dated November 3, 2020. The main analysis tool will be the *R* programming language, version 3.7.

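### Non-sorbent antidiarrheals are allowed as rescue in one place and listed as prohibited in another, and the plan does not say whether rescue costs a patient per-protocol membership

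*Protocol*

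**What the plan says.** **Allowed.** Protocol 7.3 lists among permitted treatments "Agents for relieving symptoms of acute diarrhea (in case of medical need), including electrolyte solutions, with the exception of sorbents". The synopsis and SAP 6.1 carry the same allowance, and all three leave the decision to the investigator. Protocol 5.2.3.2.5 adds that for Bristol type 6 or 7 stools at least three times a day the investigator prescribes oral rehydration and may also permit further symptomatic drugs. Two secondary endpoints count rescue use, so rescue is expected.

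**Prohibited.** Protocol 7.4 closes with "The list of prohibited medicinal products is presented in Appendix 1". The anti-diarrheal row of that appendix includes "loperamide+symeticone, loperamide, oval plantain seed coating, racecadotryl, dioctahedral smectite". It is separate from the adsorbent row and has no rescue exemption. The SAP 6.2 table repeats it: "loperamide + simethicone, loperamide, plantain oval seed coat, Racecadotril, Dioctahedral smectite".

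**The exemption.** Item 5 of 7.4 bars therapy that affects stool consistency, "excluding the drugs specified in items 3 and 4 of the" allowed-treatment list; item 4 of that list, as numbered in the synopsis, is the acute-diarrhea agents.

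**Consequence.** Exclusion criterion 12 (6.3.1) stops participation if "The patient receives/requires an additional treatment which might influence the study results" or patient safety, and points to the prohibited-therapy section. Protocol 10.8 and SAP 4.2.3 limit the PP set to patients who completed the study with no significant deviation.

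**The concern.** Rescue for acute diarrhea is given because the patient has diarrhea, so an ambiguity about rescue falls mainly on patients who have just had the primary event. If such a drug is treated as prohibited therapy, the chain from Appendix 1 through criterion 12 to the PP definition lets the outcome itself decide who stays in the PP set. The synopsis states the minimum of 208 per arm in terms of the PP population, so the PP result will carry weight. With up to 40 sites, different readings of the same pages are foreseeable, and no text says whether rescue is a significant deviation.

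**Working it through.** **Step 1: the passages side by side.**

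- The sorbent exception does not remove the conflict. Smectite appears in both the adsorbent and the anti-diarrheal rows and is barred under either reading. Loperamide and racecadotril appear only in the anti-diarrheal row.
- The time window of item 5 differs. In the synopsis it covers the 14 days before the study and the study itself. In 7.4 and the corresponding SAP 6.2 paragraph it covers only the 14 days before Visit 1.
- The exemption sits inside item 5. Appendix 1, the SAP 6.2 table and criterion 12 do not repeat it.

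**Step 2: the plan's own sample size.** Inputs from Protocol 10.3 and SAP 2.3: rates 0.26 and 0.15, two-sided alpha 0.05, power 80%, 1:1 allocation, 20% attrition.

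n = (1.960 + 0.842)² × [0.15 × 0.85 + 0.26 × 0.74] / 0.11² = 7.849 × 0.3199 / 0.0121 = 207.5, rounded up to 208. Then 208 / 0.8 = 260 per arm, 520 in all. Both figures reproduce. Power at 208 is Φ(0.11 / √(0.3199/208) − 1.960) = 0.801. Expected events are 208 × 0.26 = 54 and 208 × 0.15 = 31.

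**Step 3: removing a share f of AAD cases.** The documents give no rescue frequency, so f is an assumption. In each arm n′ = N(1 − pf) and p′ = p(1 − f)/(1 − pf); power uses the same unpooled normal approximation.

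For f = 20% in both arms from N = 208:

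- Placebo: 43.3 events among 197.2 patients, rate 0.2194.
- LRG-002: 25.0 events among 201.8 patients, rate 0.1237.
- Power: 0.723.

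| f in both arms (assumed) | Power from 208 per arm | Power from 260 per arm |
|---|---|---|
| 0% | 0.801 | 0.880 |
| 10% | 0.765 | 0.851 |
| 20% | 0.723 | 0.814 |
| 30% | 0.673 | 0.768 |
| 50% | 0.544 | 0.639 |

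The 208 column takes these losses on top of the 20% attrition already allowed for. The 260 column supposes no other losses; there, f = 20% removes 260 × 0.2 × (0.26 + 0.15) = 21 of 520 patients, about 4%. In between, if the removed cases fall within the 20% allowance and the PP set stays at 208 per arm with the depleted rates, power is Φ(0.0957 / √((0.2194 × 0.7806 + 0.1237 × 0.8763)/208) − 1.960) = 0.74.

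**Step 4: bias.** After removal the odds in an arm are p(1 − f)/(1 − p), so the odds ratio is multiplied by (1 − f placebo)/(1 − f active). With equal shares it stays at (0.26/0.74)/(0.15/0.85) = 1.99. With 30% removed on placebo and 10% on LRG-002 it is 1.991 × 0.70/0.90 = 1.55. With the shares reversed it is 1.991 × 0.90/0.70 = 2.56. Starting from 208 per arm, power is 0.363 and 0.937 respectively.

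**The case against.** The strongest reply is that Appendix 1 cannot be meant literally. Its antibacterial row lists penicillins and cephalosporins with no exemption, while inclusion criterion 3 requires an oral beta-lactam; taken at its word, it would put patients taking amoxicillin or cefixime, which 7.3 names as allowed, on a prohibited drug. The appendix must therefore be subject to the exceptions in 7.4, and the anti-diarrheal row would inherit the exemption in item 5. The synopsis wording of that item reaches on-study use. As evidence of intent this is persuasive. It does not close the gap. The antibiotic exception in 7.4 item 2 expressly covers the study period, whereas item 5 in the body and the SAP stops at Visit 1, so inheriting it from there does not settle on-study rescue.

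A reader might infer that anyone given loperamide must be withdrawn and lost from the PP set. The documents do not go that far. Criterion 12 turns on whether the treatment might affect results or safety, the PP set excludes only significant deviations, and under 11.3 the sponsor's classification of a deviation prevails, which also limits variation between sites.

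The exposed group is smaller than all AAD cases. Rescue is triggered by types 6 and 7 while the endpoint counts types 5 to 7, electrolyte solutions are expressly allowed, and additional drugs are optional.

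**Conclusion.** The inconsistency is real and stands in both documents, but it is modest. The synopsis suggests rescue was meant to be allowed; the literal chain through Appendix 1, criterion 12 and the PP definition could still exclude patients because of their outcome.

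A reader might infer that the primary result is biased because more events, and so more removals, would be on placebo. That does not follow. Equal shares leave the odds ratio at 1.99; bias needs a difference in shares between arms, and nothing in the documents shows one. Nor is PP named as the primary analysis set: Protocol 10.8 and SAP 7.1 name none, and the ITT set would keep an event recorded before withdrawal.

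The power cost is conditional. At an assumed 20% removal it is about 72% from 208 per arm or about 81% from 260 with no other losses; quoting 72% alone would add an assumed loss to a figure already net of 20% attrition. The documents also give no basis for sizing any effect on the two rescue endpoints. The case for acting is that the correction costs little and prevents outcome-dependent exclusion.

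**What to change.** Reconcile Protocol 7.3, 7.4 item 5 (including its time window), Appendix 1, exclusion criterion 12, the synopsis and SAP 6.1 and 6.2 so that they give one answer. Which drugs are permitted is for the sponsor to settle; no clinical rule is proposed here.

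Add two sentences to the SAP. First, an AAD event recorded before rescue stands. Second, investigator-prescribed rescue started after onset of the qualifying diarrhea is not by itself a significant deviation for PP membership. The second sentence concerns only the analysis set and does not decide which drugs may be used.

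The cost is a protocol clarification and a short SAP edit. No extra data are needed, since the diary already asks for the name, dose and time of symptomatic medication and the time of each stool.

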#### **7.4 Prohibited concomitant therapy**

1. Systemic glucocorticosteroids within last 8 weeks prior to and during the study;
2. Any antibacterial agents in the last 3 months prior to the study and during the study, excluding the antibacterials according to inclusion criterion 3 during the study;
3. Use of any proton pump inhibitor within 3 months prior to the study;
4. Use of other probiotics (bacteria or yeast, medications, food supplements, fermented products) and the product Broncho-munal® within 2 weeks prior to and during the study;
5. Any therapy (including medications, medical devices and food supplements) that can influence the stool consistency must not be used, according to the Investigator's opinion, within 14 days prior to Visit 1 (excluding the drugs specified in items 3 and 4 of the “Allowed Concomitant Treatments”).

The list of prohibited medicinal products is presented in Appendix 1

### **8. Efficacy Evaluation**

#### **8.1 List of efficacy parameters**

##### **Primary efficacy criterion**

Evaluation of AAD incidence from the first to the last day of LRG-002 administration vs placebo in patients with ARDs, receiving standard antimicrobial therapy. The primary efficacy criterion will be considered achieved if the odds ratio for the AAD incidence between two groups is significantly higher than 1 (i.e. AAD incidence in the LRG-002 group is lower than in placebo group).

*AAD is defined as diarrhea associated with the AB use caused by C. difficile or of otherwise not identified etiology, upon analysis of stool samples and differential diagnostics according to investigator's judgment.*

*Diarrhea is defined as loose or watery stool (Type 5-7 according to Bristol Stool Form Scale) three times a day (frequent bowel movements with formed stool is not considered as diarrhea) in accordance with WHO criteria; based on the diary data (BSFS) and confirmation of AAD by the investigator.*

## Secondary efficacy criteria

The following criteria were selected as secondary efficacy criteria of the therapy in all study groups for a comparative assessment of the therapeutic effect:

- The occurrence of bowel movements per day (according to the diary data) in the treatment group compared with the placebo group;
- The incidence of any diarrhea in the treatment group compared with the placebo group;
- The incidence of C. difficile-associated AAD in the treatment group compared with the placebo group;
- The incidence of AAD not associated with C. difficile in the treatment group compared with the placebo group;
- The duration of AAD (the time from the onset of AAD to the normalization of stool form according to BSFS (types 1, 2, 3 and 4) and the presence of normal stool within 48 hours)) in the treatment group as compared to the placebo group;
- Duration of any diarrhea (the period from the diarrhea onset to the normalization of stool form according to BSFS (types 1, 2, 3 and 4) and the presence of normal stool within 48 hours)) in the treatment group vs the placebo group;
- The changes in stool consistency (according to Bristol Stool Form Scale) (according to the diary data) in the treatment group as compared to the placebo group;
- The changes and severity of gastrointestinal symptoms, including nausea, vomiting, flatulence, abdominal pain and decreased appetite (according to the diary data) in the treatment group as compared to the placebo group;
- Change in body weight at Visit 3 compared with Visit 1 in the placebo group as compared to the treatment group;
- Hospitalization rate in the treatment group compared with the placebo group;
- The number of days of using standard symptomatic therapy (as “rescue medication”) to relieve symptoms of acute diarrhea in the treatment group as compared to the placebo group;
- The number of patients using standard symptomatic therapy (as “rescue medication”) to relieve symptoms of acute diarrhea in the treatment group as compared to the placebo group.

### 8.2 Methods and timing for evaluating, recording and analyzing efficacy parameters

The efficacy of the investigational therapy is based on diary data, laboratory and clinical data.

**Primary efficacy endpoint** – assessment of frequency of occurrence of AAD from 1 to the last day of LRG-002 administration compared with placebo in antibiotic-treated patients with ARDs, receiving standard antimicrobial therapy. The primary efficacy criterion will be considered

achieved if the odds ratio for the AAD incidence between two groups is significantly higher than 1 (i.e. AAD incidence in the LRG-002 group is lower than in placebo group).

*AAD is defined as diarrhea associated with the AB use caused by C. difficile or of otherwise not identified etiology, upon analysis of stool samples and differential diagnostics according to investigator's judgment.*

*Diarrhea is defined as loose or watery stool (Type 5-7 according to Bristol Stool Form Scale) three times a day (frequent bowel movements with formed stool is not considered as diarrhea) in accordance with WHO criteria; based on the diary data (BSFS) and confirmation of AAD by the investigator.*

**Secondary efficacy endpoints**, assessed based on the data of patient's diary include:

- The occurrence of bowel movements per day (according to the diary data) in the treatment group compared with the placebo group;
- The incidence of any diarrhea in the treatment group compared with the placebo group;
- The duration of AAD (the time from the onset of AAD to the normalization of stool form according to BSFS (types 1, 2, 3 and 4) and the presence of normal stool within 48 hours)) in the treatment group as compared to the placebo group;
- The changes in stool consistency (according to Bristol Stool Form Scale) (according to the diary data) in the treatment group as compared to the placebo group;
- The occurrence and severity of gastrointestinal symptoms, including nausea, vomiting, flatulence, abdominal pain and decreased appetite (according to the diary data) in the treatment group as compared to the placebo group;
- Duration of any diarrhea (the period from the diarrhea onset to the normalization of stool form according to BSFS (types 1, 2, 3 and 4) and the presence of normal stool within 48 hours)) in the treatment group vs the placebo group;

**Secondary efficacy endpoints**, assessed based on the data of stool analysis include:

- • The incidence of C. difficile-associated AAD in the treatment group compared with the placebo group;
- • The incidence of AAD not associated with C. difficile in the treatment group compared with the placebo group;

**Secondary efficacy endpoints**, assessed based on the clinical data include:

- Change in body weight at Visit 3 compared with Visit 1 in the placebo group as compared to the treatment group;
- Hospitalization rate in the treatment group compared with the placebo group;
- The number of days of using standard symptomatic therapy (as “rescue medication”) to relieve symptoms of acute diarrhea in the treatment group as compared to the placebo group;
- The number of patients using standard symptomatic therapy (as “rescue medication”) to relieve symptoms of acute diarrhea in the treatment group as compared to the placebo group.

